### **1.2.7. Unblinding**

This study is a double-blind design, and the study should be kept as blind as possible.

#### **1.2.7.1. Unblinding after disease progression and process**

For patients with disease progression, the subject can be unblinded according to the unblinding process if the investigator needs to know the patient's randomized drug treatment information, in order for selection of subsequent treatments:

- 1) The investigator immediately informs the sponsor's inspector;
- 2) Complete the EDC entry of the efficacy and safety data generated from the subject;
- 3) Perform source data verification (SDV) and data cleanup on the data entered in the EDC;
- 4) After data cleanup is completed, unblind the subject.

#### **1.2.7.2. Emergency unblinding**

Emergency unblinding of an individual patient is only applicable if urgent medical intervention is necessary by the investigator and continued blinding of the patient will affect the development of the best medical management for the investigator.

If emergency unblinding is required, the investigator will notify the Sponsor's medical monitor immediately to request unblinding (the investigator may perform unblinding before informing the Sponsor only if emergency treatment for the patient might be delayed). After the sponsor agrees and authorizes the IWRS, the investigator will unblind the patient. The investigator should note that the occurrence of SAEs is not a prerequisite for routine immediate unblinding. The sponsor, investigator and ethics committee of each site must be notified of the above process as soon as possible, and the unblinding time, reason and result must be recorded in the source file.

#### **1.2.8. Central review**

All imaging data collected during the study, including those obtained in unscheduled visit examinations, should be subject to independent central review (ICR) by a qualified independent review committee (IRC) in accordance with the independent imaging reading regulations. The results of this independent evaluation by the IRC will not be returned to the investigator. Efficacy endpoints derived from the IRC evaluation will be used only for sensitivity analysis.

### 1.3. Endpoint indicators

#### 1.3.1. Primary efficacy indicators

The primary endpoint of this study is PFS derived by the investigator based on the RECIST V1.1 evaluation ratings. PFS is defined as the time from the start of randomization until objective tumor progression as evaluated by the investigator or death (using the date of the first event).

#### 1.3.2. Secondary efficacy indicators

- 1) Objective response rate (ORR): As in RECIST 1.1, this is defined as the percentage of patients with at least 1 CR or PR before progression. CR and PR here do not need to be reconfirmed based on RECIST V1.1.
- 2) Duration of response (DoR): This is defined as the time from the first date on which response is met to the date of disease progression or death from other causes. The response termination date is consistent with the date used for the PFS endpoint. The start date of response time is defined as the most recent date of the first visit that meets the PR or CR criteria. If a subject does not progress after response, the duration of response will be the PFS cut-off time.
- 3) Disease control rate (DCR): Disease control rate is defined as the proportion of the subjects whose best overall response is CR, PR, or SD. Considering the 7-day visit window, the requirement for the evaluation of SD is that the time from the first medication to the final overall efficacy evaluation result of SD prior to progression be at least 35 days.
- 4) Depth of response (DepOR): As a continuous variable, this refers to the change in the sum of the length of the longest diameter of the target lesion as defined by RECIST 1.1 when no new lesions appear or there is no progression of non-target lesions versus baseline. The change in tumor size of a subject during a visit includes absolute change (mm) and relative change (%). The percentage change in tumor size of the subjects with measurable lesions at baseline will be calculated based on the percentage changes in the total diameters of target lesions compared with those measured at baseline at each visit. The optimal value of depth of response will be generated from all of the efficacy evaluations before progression or before the start of subsequent anti-tumor treatment. The calculation formulae for absolute change and relative change are as follows:
  - a) Absolute change in tumor size = the sum of the longest diameters of all of the subject's measurable target lesions at the visit (if the target lesion site is a lymph node, use the maximum short diameter) - the sum of the longest diameters of all target lesions at baseline (if the target lesion site is a lymph node, use the maximum short diameter)
  - b) Percentage change in tumor size relative to baseline = (the sum of the longest diameters of all of the subject's measurable target lesions at the visit (if the target lesion site is a lymph node, use the maximum short diameter) - the sum of the longest diameters of all target lesions at baseline (if the target lesion site is a lymph node, use the maximum short diameter)) / the sum of the longest diameters of all target lesions at baseline (if the target lesions site is a lymph node, use the maximum short diameter) \* 100%
  - c) Optimal value of depth of response = minimum value of percentage change in tumor size versus baseline

5) Overall survival (OS): This is defined as the time from the start of randomization to the date of death from any cause.

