12.1.7 Depth of Response (DepOR)

According to RECIST 1.1, depth of response (change in tumor size) is defined as the change in the sum of the longest diameters of target lesions in the absence of new lesions or progression of non-target lesions from baseline. The percentage change in tumor size for patients with measurable disease at baseline will be calculated using the percentage change in the sum of target lesion diameters from baseline at each visit. The best depth of response will be generated from all response evaluations prior to progression or prior to initiation of subsequent anti-tumor therapy.

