### 2.2.8. Missing data processing

In general, missing values are not filled in unless specifically indicated.

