#### 4.4.4. Depth of response (DepOR)

The following analysis of this indicator is performed based on the FAS.

- 1) Based on visit, the number of subjects included in the calculation and absolute change and relative percentage change in tumor size versus baseline in the two treatment groups are descriptively summarized. At the same time, the means, standard deviations, 1/4 quantiles, medians, 3/4 quantiles, minimums, and maximums are also given.
- 2) The best percentage of tumor response by treatment group is summarized. The number of subjects included in the calculation and the mean, standard deviation, minimum, maximum, and median of the best percentage in each treatment group are given; and the numbers and proportions of subjects who achieved a 30%, 50%, and 75% tumor response are calculated.
- 3) The ANCOVA model is adopted for comparison of best percentage of tumor response between groups. The covariates in the model include EGFR mutation type, brain metastasis status, the sum of the diameters of all evaluable target lesions at baseline (mm), and the time interval from the baseline scan date to the date of randomization (days). The analysis results provide the number of subjects included in the calculation, the corrected mean best percentage, and the corresponding 95% confidence interval of each treatment group. At the same time, the estimated least squares mean of the comparison between the two groups, the 95% confidence interval, and the test p value are given (level of significance of 0.05).
- 4) Waterfall plots of best percentage of tumor response by treatment group are drawn. In the plots, two reference lines of the best percentage are marked: 20% (indicating a 20% increase in tumor size versus baseline, corresponding to disease progression as defined by RECIST V1.1) and -30% (indicating a 30% decrease in tumor size versus baseline, corresponding to partial response as defined by RECIST V1.1).

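### Best depth of response is taken only from pre-progression scans, so patients who progress at their first scan have no value and fall out of an analysis labelled FAS

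*SAP*

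**What the plan says.** - **Which scans count.** Protocol 12.1.7 has the best depth of response "generated from all response evaluations prior to progression or prior to initiation of subsequent anti-tumor" therapy. SAP 1.3.2(4) has it "generated from all of the efficacy evaluations before progression or before the start of subsequent anti-tumor treatment" and defines the best value as the minimum percentage change from baseline.
- **Visit-level restriction.** The same SAP item counts a change only "when no new lesions appear or there is no progression of non-target lesions versus baseline". Protocol 12.1.7 has a matching condition.
- **Between-arm analysis.** SAP 4.4.4 sets the endpoint on the FAS. "The ANCOVA model is adopted for comparison of best percentage of tumor response between groups". Of the ANCOVA it adds: "The analysis results provide the number of subjects included in the calculation". It also asks for the proportions reaching 30%, 50% and 75% response, without naming a denominator, and for a waterfall plot.
- **Waterfall reference line.** One of the two lines is at "20% (indicating a 20% increase in tumor size versus baseline, corresponding to disease progression as defined by RECIST V1.1").
- **Missing values.** SAP 2.2.8: "In general, missing values are not filled in unless specifically indicated". Nothing is indicated for depth of response.
- **First scan.** Protocol 10.2.1 schedules the first tumor assessment 6 weeks after randomization, with a window of 1 week either side.

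**The concern.** A patient who progresses at the first post-baseline scan has no earlier post-baseline evaluation. Under the written rule that patient has no best value, none is imputed, and the ANCOVA becomes a complete-case analysis. Inclusion then depends on an outcome that arises after randomization and that treatment may influence. The analysis no longer covers the FAS that it names.

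These patients are not hypothetical. SAP 4.2 plans a sensitivity analysis of PFS because it expects some primary resistance, which it defines as progression within 3 months.

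At stake are the mean shrinkage in each arm, the adjusted difference between arms and, depending on the denominator chosen, the 30/50/75% proportions.

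**Working it through.** **1. Reproduce the design.** No sample-size figure is given for depth of response, so the check starts from the PFS design (protocol 5.3, SAP 1.2.3): HR 0.67, two-sided alpha 0.05, power 90%, 1:1, medians 10 and 15 months, exponential, 8 months' accrual, 23 months in total.
- Events (Schoenfeld) = 4 × (1.960 + 1.282)² / (ln 0.67)² = 262.06, against 262 stated.
- Event probabilities with uniform accrual and no dropout: 0.729 (gefitinib) and 0.582 (HS-10296), mean 0.655. N = 262 / 0.655 = 400, within 3% of the stated 410.

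The stated medians therefore fit the plan's own figures and can be used below.

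**2. Share with a PFS event by the first scan.** Formula: 1 − 2^(−t/median), with t = 42 / 30.4375 = 1.380 months (month length from SAP 2.2) and 410 / 2 = 205 patients per arm.

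| First scan | Gefitinib | HS-10296 |
|---|---|---|
| Week 5 | 7.7% (15.7 patients) | 5.2% (10.6) |
| Week 6 | 9.1% (18.7) | 6.2% (12.7) |
| Week 7 | 10.6% (21.6) | 7.2% (14.7) |

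The gap at week 6 is 2.9 percentage points. For patients scanned on schedule, each share is an upper limit on what the rule removes, because it includes deaths without a scan, which have no value under any rule.

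**3. Effect on the means.** If the lost patients' mean change is g points worse than that of the others, leaving them out overstates mean shrinkage by share × g. The documents give no value for g; 30 to 70 points is an assumption, taken as equal in both arms.

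| g | Gefitinib | HS-10296 | Reduction in difference |
|---|---|---|---|
| 30 | 2.7 | 1.9 | 0.9 |
| 50 | 4.6 | 3.1 | 1.5 |
| 70 | 6.4 | 4.3 | 2.1 |

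A wider set of assumptions (g from 40 to 100 points, scan at week 5 to 7) gives 1.0 to 3.4 points.

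**4. The +20% line.** At the first scan the reference for target-lesion progression is the baseline sum. Protocol Appendix D, Table 2, calls it progression when the sum rises by at least 20% and at least 5 mm. Such a scan is excluded by the rule, so a plotted best value of +20% or more needs a rise of at least 20% but under 5 mm. That requires a baseline sum below 5 / 0.20 = 25 mm.

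**5. Would counting the progression scan disturb other patients?** Not for target-lesion progression. The best value is a minimum, and a progressing target sum lies above the smallest earlier sum. A patient who already has a value keeps it.

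**The case against.** **The loss is visible.** SAP 4.4.4 requires the analysed number for the by-visit summaries, the best-percentage summary and the ANCOVA. SAP 4.4.1 tabulates best response, including PD and NE, on the FAS. This stands: the plan does not conceal the number. It does not ask why values are missing, or for the reasons by arm.

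**The wording may allow the progression scan.** The alternative about subsequent therapy could be read as admitting it when no new therapy has begun, and the +20% line may show that this was intended. A reader might infer that the SAP contradicts itself. It need not: a reference line does not require bars beyond it, and small baseline sums can reach it. But even on the generous reading, first-scan progression by new or non-target lesions stays excluded by the visit-level restriction. A tested endpoint should not have two readings.

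**More loss on gefitinib is not established.** A reader might take it as fact. No section says so; it follows from extending the planned medians back to day 42. SAP 4.2 describes primary resistance for EGFR TKIs as a class and doubts proportional hazards early on. If early progression is equal in the arms, the between-arm shift largely disappears, although both means are still overstated.

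**Not every lost patient is a poor responder in the target lesions.** Protocol 10.2.1 and Appendix D 4.3 allow non-target progression with stable or shrinking target lesions, so the assumed gap would not apply to all of them. This stands, and is a further reason to treat the figures as limits.

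**Inflated 30/50/75% proportions are not shown.** The denominator is unstated, so the documents support only the criticism that it is unspecified.

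**Conclusion.** The point holds as a gap in the derivation rule. Following both documents as written, first-scan progressors have no best depth of response and leave an ANCOVA and waterfall plot described as FAS. The upper limit is about 19 gefitinib and 13 HS-10296 patients of 205 each at day 42, given exponential PFS with the planned medians and no dropout.

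With an assumed gap of 30 to 70 points, mean shrinkage is overstated by up to 2.7 to 6.4 points on gefitinib and 1.9 to 4.3 on HS-10296. The difference is reduced by up to about 0.9 to 2.1 points. That direction is conservative for HS-10296, but it depends on the expected imbalance actually occurring.

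The effect is modest and confined to a secondary endpoint. The primary PFS analysis is unaffected. It should be corrected because the rule selects patients on a post-randomization outcome and the remedy is cheap.

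**What to change.** In SAP 1.3.2(4) and 4.4.4, and in protocol 12.1.7:

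1. Take the best percentage change from post-baseline assessments up to and including the first progression assessment, and before any subsequent anti-tumor therapy.
2. Where the first post-baseline scan is progression by new or non-target lesions and there is no earlier value, use the measured target-lesion sum at that scan and flag it. Leave patients with a pre-progression value unchanged. Using the target sum at every such progression would redefine the endpoint for patients who already have a value.
3. Use all FAS patients as the denominator for the 30/50/75% proportions, counting those with no value as not reaching the threshold.
4. Report the number of missing values and the reasons, by arm.
5. Keep the pre-progression-only version as a sensitivity analysis.

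Step 1 also makes the +20% waterfall line meaningful.

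**Cost.** A wording and derivation change, including a stated exception to the visit-level restriction. Target-lesion measurements by visit are already planned (SAP List 16.2.6.3). Mean shrinkage will look slightly less favourable in both arms. Patients with no post-baseline scan, or with no target measurement at the progression scan and no earlier value, remain missing from the ANCOVA.

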### 1.3.3. Safety Evaluation Indicators

The safety endpoints include:

- 1) Adverse events and serious adverse events
- 2) Laboratory testing
  - Clinical blood biochemistry: Albumin, ALT, AST, alkaline phosphatase, bilirubin, total bilirubin, calcium, total blood calcium, creatinine, creatine kinase, glucose, LDH, HbA1C, magnesium, potassium, sodium, urea nitrogen or urea (pick one of two)
  - Hematology: Hemoglobin, white blood cells, hematocrit, red blood cell count (RBC), absolute white blood cell count (neutrophils, lymphocytes, monocytes, basophils, eosinophils), platelet count, reticulocyte count
  - Urinalysis: Glucose, urine protein, blood in urine
- 3) Vital signs: Pulse, sitting systolic and diastolic blood pressure, respiratory rate, and body temperature.
- 4) Physical examination: Including general condition, skin and mucous membranes, lymph nodes, head, neck, chest, abdomen, spine, and limbs or other examinations.
- 5) Weight
- 6) 12-lead electrocardiogram (ECG): Heart rate (beats/minute), QRS duration (ms), PR interval (ms), RR interval (ms), QT and QTcF intervals (ms), and clinical classification of normal/abnormal ECG.
- 7) ECOG Performance Status Score
- 8) LVEF Measured With Echocardiography or MUGA
- 9) Changes of ophthalmological examination

## **2. General analysis definition**

### **2.1. Statistical analysis software**

Shanghai Hansoh BioMedical Co., Ltd., is responsible for the statistical analysis of this trial. SAS 9.4® or a newer version of the software is adopted for the statistical analysis.

### **2.2. General principles and analytical definitions**

The biostatistician and principal investigator formulate the statistical analysis plan, which is finalized before data are locked, based on the study protocol.

- 1) For the time interval, days are converted into months at one month = 30.4375 days.
- 2) Efficacy analysis is performed in the full analysis set (FAS) and the per-protocol set (PPS). The results are based on the full analysis set. Safety analysis is performed in the safety set (SS).
- 3) Except for special circumstances, the statistical diagrams are only for planned visit points, while the data sheets list all visits, including unplanned visits.

#### **2.2.1. Descriptive statistics**

For continuous variables, arithmetic mean, standard deviation (SD), median, minimum, and maximum are used to describe the data. The number of decimal places for minimum and maximum will be consistent with the raw data recorded in the database. Mean and median will keep one more decimal place than the raw data recorded in the database. Standard deviation will keep two more decimal places than the raw data recorded in the database.

Categorical variables will be listed in the form of frequency tables (frequency and percentage). Percentages will be rounded to one decimal place. When the frequency is 0, frequency (composition ratio) will not be shown.

For time outcome endpoint indicators, the number of people who reached the event endpoint, the number of people censored, and the estimated 25%, median, and 75% quantiles of the indicators and their 95% confidence intervals will be given and the Kaplan-Meier curves of the two treatment groups will be drawn.

#### **2.2.2. Hypothesis testing**

Otherwise specified, all statistical inferences are tested using a two-tailed test or two one-tailed tests, with a statistical significance level of  $\alpha = 0.05$ , and the interval of the parameters is estimated using 95% confidence interval. The p value will retain 4 decimal places, and when the p value is less than 0.0001, it is recorded as “< 0.0001”. 95% confidence interval will keep one more decimal place than the raw data recorded in the database. The confidence interval of rates is estimated with the exact probability test.

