5.1.2 Secondary Objectives

- 1) To compare the following anti-tumor efficacy measures of HS-10296 versus gefitinib: overall survival (OS), objective response rate (ORR), duration of response (DoR), disease

control rate (DCR), and depth of response (DepOR).

2) To compare the safety of HS-10296 versus gefitinib.

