#### 1.1.2. Secondary objectives

- 1) To compare the other anti-tumor efficacy of HS-10296 treatment versus gefitinib treatment: Overall survival (OS), objective response rate (ORR), duration of response (DoR), disease control rate (DCR), and depth of response (DepOR).
- 2) To compare the safety of HS-10296 and gefitinib treatment.

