The log-rank test stratified by EGFR mutation type and brain metastasis status will be used to compare the PFS distributions of the HS-10296 group and the gefitinib group to determine whether there are statistical differences. This test is a two-tailed test with a level of significance of 0.05. The results will be given as test p values.

Kaplan-Meier plots of the two treatment groups are drawn and the 1/4 quantile, median value, and 3/4 quantile of the PFS of the two treatment groups as well as the 95% confidence intervals for each quantile are given. The Kaplan-Meier estimates of progression-free survival at 6, 12, 18, and 24 months as well as the 95% confidence intervals corresponding to the K-M estimates based on Greenwood's standard error estimation method are given.

The stratified Cox proportional hazards model is used to estimate the PFS hazard ratio (HR) of the two treatment groups and the 95% confidence intervals corresponding to the estimates are given. The reasonableness of the proportional hazards assumption in this model will be tested.

The above two tests use subjects' actual stratification information during the screening period for analysis.

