#### 4.4. Secondary Efficacy Endpoint Analysis

##### 4.4.1. Objective response rate (ORR)

The following analysis of the endpoint will be performed based on the FAS:

- 1) The number and percentage of best tumor response results based on treatment group are summarized as follows: Complete response (CR), partial response (PR), stable disease (SD), progressive disease (PD), and not evaluable (NE).
- 2) The number of cases that achieved an objective response and the objective response rate (as a percentage) as well as the 95% Clopper-Pearson confidence interval for the response rate in each treatment group are calculated and summarized. In ORR analysis, evaluations performed after subject progression are not included in the analysis. If a subject uses other non-investigational drugs for anti-tumor therapy after terminating the investigational drug treatment, any CR or PR occurring from the time of use will not be included in the numerator of the ORR calculation.
- 3) A logistic regression model stratified by EGFR mutation type and brain metastasis status is used for the Wald Chi-squared test to compare the objective response rates of the two treatment groups. The odds ratio (OR) estimate and 95% confidence interval calculated based on the Wald method are given.

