#### 4.4.3. Disease Control Rate (DCR)

The following analysis of DCR based on the FAS will be performed:

- 1) Descriptive summarization of DCR by treatment group is performed. The DCR estimate and 95% Clopper-Pearson confidence interval of each treatment group is estimated.
- 2) A logistic regression model stratified by EGFR mutation and brain metastasis status is adopted to compare the DCR of the two treatment groups. The estimated odds ratio (OR), 95% confidence interval, and test p value of DCR of the two treatment groups are given.

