#### 4.4.5. Overall survival (OS)

Overall survival OS is performed separately in the FAS and PPS.

If the subject's date of survival or death is confirmed to be later than the data cutoff date, the survival period of the subject is censored to the data cutoff date. If it is not known whether the subject has died, it will be censored to the latest known date of survival recorded in the EDC.

- 1) The same method as the primary endpoint PFS is adopted for analysis. The Kaplan-Meier estimates of overall survival rate at 12, 24, and 36 months and corresponding 95% confidence intervals are given.
- 2) If the data are mature, the same subgroup analysis method as PFS will be adopted for analysis of OS.

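### Five secondary endpoints each get a between-arm test at a default 0.05 with no gate, order, alpha split or nominal label; if each p<0.05 is read as a claim, the family error is about 13% to 23%.

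*SAP*

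**What the plan says.** The primary test is fully specified. SAP 4.1 compares investigator-assessed PFS in the full analysis set by a stratified log-rank test and adds: "This test is a two-tailed test with a level of significance of 0.05".

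The secondary objective is comparative. Protocol 5.1.2 reads "To compare the following anti-tumor efficacy measures of HS-10296 versus gefitinib", and SAP 1.1.2 lists the same five: "Overall survival (OS), objective response rate (ORR), duration of response (DoR), disease control rate (DCR), and depth of response (DepOR").

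SAP 2.2.2 sets the general rule: "all statistical inferences are tested using a two-tailed test or two one-tailed tests, with a statistical significance level of" 0.05, with 95% confidence intervals. The sentence opens with a qualifier that allows other specifications, so 0.05 is a default for each test.

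SAP 4.4 plans a between-arm comparison for every secondary endpoint:

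- **ORR (4.4.1):** a stratified logistic model "is used for the Wald Chi-squared test to compare the objective response rates of the two treatment groups", with a 95% Wald interval for the odds ratio.
- **DoR (4.4.2):** the PFS method, in responders.
- **DCR (4.4.3):** a stratified logistic model; the odds ratio, "95% confidence interval, and test p value of DCR of the two treatment groups are given".
- **DepOR (4.4.4):** ANCOVA; the adjusted difference, its 95% interval "and the test p value are given (level of significance of 0.05").
- **OS (4.4.5):** "The same method as the primary endpoint PFS is adopted for analysis", in both the full analysis set and the per-protocol set.

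Protocol 12.3.2.2 plans the same comparisons. It makes the OS analysis depend on an event requirement for which it gives no number.

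Neither document contains a gate on PFS, a testing order, an alpha split, a multiplicity adjustment, or a statement that the secondary tests are nominal, exploratory or descriptive.

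**The concern.** The plan does more than leave multiplicity unmentioned. It assigns 0.05 to each test by default and repeats that level for one secondary endpoint, DepOR. A secondary p-value of 0.04 would therefore meet the SAP's own significance criterion whatever the PFS result and however many other secondary tests had been run. With five such tests, a single significant secondary result is much weaker evidence than its p-value suggests. At stake is how the secondary results may be described in the report, and whether a lone positive one can be presented as confirmed. The primary conclusion is not at stake.

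**Working it through.** **1. Primary test: does the stated level reproduce the plan's figure?** Inputs from Protocol 5.3 and SAP 1.2.3: HR 0.67, 1:1 allocation, 90% power, two-sided alpha 0.05, 262 events. The Schoenfeld formula is d = 4(z_α + z_β)² / (ln HR)².

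- Two-sided 0.05: 4 × (1.960 + 1.2816)² / (ln 0.67)² = 262.06. The stated 262 is reproduced; power at 262 events is 0.8999.
- Two-sided 0.10 would give 213.6, that is 214 events.

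So the primary test was sized at two-sided 0.05, as SAP 4.1 says. It is a single test, and its type I error does not depend on what is done with the secondaries.

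**2. Secondary family.** Inputs: k = 5 endpoints (SAP 1.1.2), each at 0.05 (SAP 2.2.2, 4.1 and 4.4). Assumptions not in the documents: all five nulls are true, every p<0.05 is read as a claim, and each test has its nominal size.

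- Independent tests: 1 − (1 − 0.05)^5 = 22.6%.
- Upper bound under any dependence: 5 × 0.05 = 25%.

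**3. Allowance for correlation.** ORR, DCR and DepOR are built from the same tumour assessments, so positive correlation is likely, but the documents give no value. The table shows the simulated probability of at least one |Z| > 1.96 among equicorrelated normal statistics (2 million draws).

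| Assumed common correlation | Five tests | Four tests (OS not tested) |
|---|---|---|
| 0 | 22.6% | 18.5% |
| 0.3 | 20.9% | 17.4% |
| 0.5 | 18.3% | 15.6% |
| 0.8 | 12.7% | 11.4% |

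The four-test figure at correlation 0 is 1 − 0.95^4 = 18.5%. The column applies if the event requirement in Protocol 12.3.2.2 is not met and OS is not tested.

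**4. With control.** In a fixed sequence at two-sided 0.05, no test is performed after the first non-significant one. A false claim therefore requires the first true null in the order to be rejected, and the family error is at most 5%. For comparison, Bonferroni at 0.01 each gives 1 − 0.99^5 = 4.9% if independent, and at most 5% in any case.

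**5. Sidedness wording in SAP 2.2.2.** Two one-sided tests at 0.05 each would amount to two-sided 0.10. OS and DoR inherit two-tailed 0.05 from the PFS method, so that reading could reach only ORR, DCR and DepOR. With those three at 0.10 and the other two at 0.05, the five-test probability would be 27.8% at correlation 0.5. The next section explains why this reading is strained.

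**The case against.** The documents name one primary endpoint, size the trial on it alone and list the rest as secondary. Planning a p-value is not planning a confirmatory claim, and 0.05 is a per-test default that nobody promised would hold across the family. All of that stands. A reader might infer that the plan undertakes to hold 5% for the secondaries and breaks it, or that it licenses a superiority claim on a secondary endpoint when PFS fails. The documents contain neither the promise nor such a claim rule. What they lack is any statement the other way, and the p<0.05 criterion is there to be used.

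Three stronger readings of the size also fail:

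- **A single figure of 18%.** Five tests give about that value only at an assumed common correlation near 0.5, which the documents do not supply. Only a range, labelled as an assumption, can be defended.
- **Five full-size tests are certain.** The OS test may not take place. DCR may also sit close to its ceiling. Protocol 4.2.4 reports 97.2% at 110 mg in second-line patients. If that rate held in both arms with 205 per arm (410/2), the Wald test's actual size would be about 2.3%; at 90% it would be about 4.8%. The range above is therefore somewhat high if DCR is near its ceiling.
- **The one-tailed wording is a second error-rate problem.** The ORR test is a one-degree-of-freedom Wald chi-squared, which is non-directional. The DCR and DepOR p-values are paired with 95% intervals, and SAP 2.2.2 itself prescribes 95% intervals. The phrase can equally mean 0.025 on each side. It is loose wording to tidy.

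None of this supplies a gate, an order or a label.

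**Conclusion.** The point holds as a gap in the rules for secondary inference. Five between-arm tests are planned at a default 0.05, and nothing says which of them, if any, can support a claim. If all five nulls are true and each p<0.05 is treated as a claim, the chance of at least one false claim is about 13% to 23% for assumed common correlations from 0.8 down to 0. Without OS it is about 11% to 19%. Every value in these ranges is more than twice the per-test level, so the need for a rule does not depend on the correlation chosen. The structure can be checked directly in the text; the size rests on the stated assumptions. The type I error of the primary PFS test is not affected.

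**What to change.** Make the change before data lock, which is the SAP's own milestone for finalization (SAP 2.2). Unblinding is not a usable deadline, because both documents allow individual patients to be unblinded at progression.

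1. In SAP 2.2.2 and 4.4, state that only the primary PFS test is confirmatory, and that secondary p-values are nominal and support no claim of statistical significance.
2. Alternatively, test the secondaries in a fixed order at two-sided 0.05, entered only if PFS is significant and stopped at the first non-significant result, with everything after that nominal. The order must be written out, since it is the substance of the rule.
3. In SAP 4.4.4, remove the stated 0.05 level or tie it to the rule chosen.
4. As a tidy-up only, delete the reference to two one-tailed tests in SAP 2.2.2, so that all tests are two-sided at 0.05 and agree with the 95% intervals.

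The cost is a few sentences, with no new patients, data or analyses. The price is that secondary results that are nominal, or that fall after a failed step, cannot be called statistically significant.
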